## Background

Water exchange (WE) colonoscopy is a standardized technique developed to achieve gasless colonoscope insertion. WE maximizes colon cleanliness and improve the adenoma detection rate (ADR). The American Society for Gastrointestinal Endoscopy has recommended using sterile water during gastrointestinal endoscopy and this form the basis of standard protocol at most endoscopy units. However, increased mucus production in the left colon is anecdotally observed during withdrawal of water-aided colonoscopy.

In a recent pilot study, El Rahyel et al. reported normal saline infusion significantly reduced left colon mucus production compared to sterile water during water-aided colonoscopy. This finding is promising for future WE practice. However, in that pilot study, the insertion method was not WE, the patients were not randomized, and the effect of saline infusion on serum electrolyte was not examined. Therefore, the provocative finding warrants validation.

The primary aims of this study are to compare the left colon mucus scores between colonoscopy using carbon dioxide (CO2) insufflation and WE, and in those patients undergoing WE, the scores between groups using warm water versus warm mixed saline/water infusions during insertion. We hypothesize that the mucus scores would be lower when saline is used during WE insertion.

## Methods

This will be a prospective, randomized, controlled trial comparing left colon mucus scores between CO2 insufflation, WE insertion with water (WE water group), WE insertion with 1:1 mixed normal saline/water (WE 50% saline group), and WE insertion with 1:3 mixed normal saline/water (WE 25% saline group). The mucus score will be graded during withdrawal by blinded colonoscopists and research assistant. It will be conducted at Evergreen General Hospital in Taoyuan, Taiwan. Consecutive patients will be enrolled

Date: 02/01/2021

from March 2021 to July 2022. A written informed consent will be obtained from all participating patients. The study has obtained approval from Institutional Review Boards and has been registered with *ClinicalTrials.gov* (NCT04769739).

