## **Colonoscopy Procedures**

Colonoscopies will be performed by two board-certified colonoscopists who

have experience in WE ([name], [name]). The colonoscopist is blinded as to whether water or mixed saline/water is being used. Standard colonoscopes (CF-Q260AL/I, CF-HQ290L/I; Olympus Medical Systems Corp., Tokyo, Japan) will be used.

Antispasmodic medication will be administered during colonoscopy examination if indicated. All infused fluids will be warmed to approximately 32-33 °C. CO2 insufflation will be used for CO2 group and during the withdrawal phase of the WE group. Colonoscopy will begin with the patients in the left lateral position. In the WE group, the air pump will be turned off before starting the procedure. During the insertion phase, air and residual water or feces in the rectum will be aspirated, and then the colon will be irrigated with warm fluid using a flushing pump (Olympus AFU-100; Olympus Corp.). There will be no restriction placed on the overall volume of fluid infused to achieve adequate cleansing. WE entails the infusion of fluid to open the lumen and suction of infused fluid sequentially. Air pockets, when encountered, will be aspirated. When the cecum is reached and after most of the fluid is suctioned to collapse the cecal lumen, CO2 will be opened. Cecal intubation will be defined as the passage of the scope tip beyond the ileocecal valve with visualization of the medial wall between the ileocecal valve and the appendix orifice.

Polyp search and resection will be performed during the withdrawal phase in all groups. Insertion polypectomy will not be performed. All proximal colon (defined as the colon segment proximal to the descending colon) polyps will be removed irrespective of their size and appearance. All diminutive polyps with hyperplastic appearance (based on narrow band imaging) in the rectosigmoid colon will be documented by photography and left alone. Polyp size will be determined by comparison with an opened biopsy forceps or a snare.

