In all groups, the following information will be recorded: bowel preparation quality using the Boston Bowel Preparation Scale score; the total amount of sedative medications; the length of colonoscopy reaching cecum; the amount of fluid infused and suctioned during insertion and withdrawal phases; the insertion time; the withdrawal time; the need of abdominal compression and/or position change to assist colonoscopy insertion; and the overall polyp number,

size, histology and location.

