### **Mucus scores**

During the withdrawal phase of the colonoscopy, the blinded colonoscopist and another blinded research assistant will grade the amount of mucus produced in the left colon (descending colon, sigmoid colon, rectum) independently. No validated scoring system for the mucus production in the colon is available. We use a 5-point Colon Mucus Scale (CMS) (0-4 points), modified from the original colon mucus study by El Rahyel et al., to quantitate the amount of mucus production in left colon: score 0: no visible mucus; score 1: minimal amounts of clear mucus in thin streaks or strands; score 2: mild opaque mucus in thin strands; score 3: moderate opaque mucus in thicker clumps covering one side of surface; score 4: more opaque mucus in thicker clumps covering more views of lumen (Figure 1). Prior to beginning scoring, the colonoscopists and study assistant will review 10 videos and discuss their scores. After they have reached consensus on the 10 cases, scoring will be performed independently.

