### **Outcomes**

The primary outcomes are the left colon mucus scores using CMS between colonoscopy using CO2 insufflation and WE, and, in those patients undergoing WE, the scores between groups using water versus 50% saline versus 25% saline. Secondary outcomes include procedure times (insertion and withdrawal times) and acute serum electrolyte abnormality in the WE saline groups. Patients assigned to the WE saline groups will receive measurements of the serum sodium, potassium, and chloride, which will be performed 20 minutes before and 60 minutes after the colonoscopy.

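### Raters are called blinded without qualification, but the colonoscopist is blinded only to fluid type, and the plan does not say which of two mucus scores is analysed for CO2 versus water exchange

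*Combined protocol and SAP*

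**What the plan says.** There is one document, the combined protocol and SAP. Methods introduces the outcome assessment without any limit on blinding: "The mucus score will be graded during withdrawal by blinded colonoscopists and research assistant". Mucus scores repeats this, saying that "the blinded colonoscopist and another blinded research assistant will grade the amount of mucus produced in the left colon", with the two scoring independently after a training set of 10 videos. Statistical analysis again calls the raters blinded when it plans a kappa for their agreement.

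Colonoscopy Procedures gives the scope: "The colonoscopist is blinded as to whether water or mixed saline/water is being used". The same section has two colonoscopists perform the examinations and describes an insertion that differs visibly by method: "In the WE group, the air pump will be turned off before starting the procedure", followed by infusion and suction of fluid, with CO2 opened only at the cecum. The CO2 group is insufflated. On withdrawal, CO2 is used in every group.

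CO2 versus WE is a primary comparison in two places. Background says: "The primary aims of this study are to compare the left colon mucus scores between colonoscopy using carbon dioxide" (insufflation) and WE. Outcomes says: "The primary outcomes are the left colon mucus scores using CMS between colonoscopy using" CO2 insufflation and WE, followed by the comparison among the WE fluids.

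**The concern.** A contrast between water and saline mixtures exists only inside the WE arms. Blinding to it tells us nothing about CO2 versus WE, and whoever inserts the scope cannot fail to know which method is in use. If that person also grades, one of the two scores per patient is unblinded for a primary comparison, while three sections describe it as blinded.

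This matters because the outcome is a judgement. The plan itself says: "No validated scoring system for the mucus production in the colon is available". The cut used in the analysis, 0–1 versus 2–4, turns on whether thin mucus looks clear or mildly opaque. A small expectation effect at that boundary would move patients across it.

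The second rater could resolve this, but Mucus scores, Outcomes and Statistical analysis do not say whether the colonoscopist's score, the assistant's score, a mean or a consensus is analysed. Kappa measures agreement; it does not choose a score.

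**Working it through.** **The text, side by side**

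1. Methods, Mucus scores and Statistical analysis: raters blinded, no limit given.
2. Colonoscopy Procedures: colonoscopist blinded to fluid type only.
3. Who inserts: the two colonoscopists. Who grades: the colonoscopist and a research assistant, during withdrawal. No section describes a handover at the cecum, a withdrawal-only grader or masked video reading of trial patients. That the inserting colonoscopist grades is therefore the natural reading, but an inference.
4. Score analysed: not named in any section.
5. How the assistant is kept from seeing the insertion: not stated. Nor is it stated who handles the fluid or records "the amount of fluid infused and suctioned during insertion and withdrawal phases".

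**Illustration of size**

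The plan gives no figure on this point to reproduce. Inputs taken from it are 68 evaluable patients per arm, the planning rates for a score of 1 or less (50% WE water, 80% WE 50% saline; Sample size estimation), Fisher's exact test, the 5% level, and pairwise tests only after a significant overall test (Statistical analysis). Assumptions not in the plan: two-sided testing; a CO2 rate p equal to the true WE rate; and a share b of WE patients with a true score of 1 or less being graded 2 or higher.

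The observed WE rate is then p(1 − b). At b = 10% this is 0.50 × 0.90 = 0.45, or 0.80 × 0.90 = 0.72.

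False-positive rate, CO2 versus one WE arm (68 v 68), without the gate:

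Σᵢ Σⱼ Bin(i; 68, p) × Bin(j; 68, p(1 − b)) × 1[Fisher P < 0.05]

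With the gate, the overall four-arm test must be significant as well. This was simulated with the three WE arms equal and a chi-square test standing in for the overall Fisher test.

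| b | p = 50%, no gate | p = 80%, no gate | p = 50%, gated | p = 80%, gated |
|---|---|---|---|---|
| 0 | 3.2% | 3.1% | about 1.6% | about 1.5% |
| 2% | 3.3% | 3.6% | – | – |
| 5% | 3.9% | 6.0% | about 2.0% | about 3.1% |
| 10% | 6.2% | 14.7% | about 3.5% | about 9% |

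If the WE arms truly differ, as the trial hopes, the overall test will often be significant anyway and the gate protects less. The gated and ungated columns are then best read as a range.

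**The case against.** The plan is short, and a fair reader may take blinded in three sections as shorthand for the scope that Colonoscopy Procedures states. No sentence claims that the operator is blind to CO2 versus WE. An operator cannot be blinded to the insertion method, and the plan responds sensibly by adding a second, independent rater on every case. The only stated hypothesis and the only powered comparison concern the WE fluids. Grading by the colonoscopist who did not insert is not excluded.

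Most of this stands, and it limits the point. It does not remove it: the second rater helps only if that score is the one analysed, and CO2 versus WE is listed first among the primary aims and outcomes, whether or not it is powered.

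A reader might infer more than the documents support:

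- *That the research assistant is unblinded too.* The plan calls the assistant blinded and nothing contradicts it. Only the means is missing.
- *That the powered comparison is compromised.* The colonoscopist is blinded to fluid type, so comparisons within WE are not affected through the operator.
- *That false positives rise about fivefold.* CO2 against all WE patients pooled (68 v 204), at a true rate of 80% and b = 10%, gives 23.4%, or 23.4/5 = 4.7 times the nominal level. But Statistical analysis names no pooled test, and this figure needs every WE arm at 80% when water is planned at 50%. With WE rates of 50%, 80% and 77% (the last from Table 1) and CO2 at their mean, (50 + 80 + 77)/3 = 69%, the pooled figure is 15.8%.
- *That the bias would favour CO2.* Background reports more mucus with water-aided colonoscopy as an anecdotal observation and states no hypothesis for CO2 versus WE. The direction is an assumption.

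**Conclusion.** The concern holds in a limited form and should be fixed. Two parts are certain from the text: the stated scope of blinding is inconsistent between sections, and the analysed score is unnamed. The second gap touches every primary comparison as a matter of definition. The third part, that the operator is the grader, is held with medium confidence.

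Together they allow an unblinded score to be analysed for CO2 versus WE and reported as blinded. The consequence runs from negligible (2% misgrading) to a false-positive rate of 6.2% to 14.7% ungated, or about 3.5% to 9% gated with equal WE arms, at 10% misgrading. The gated figures compare with about 1.5% when nothing is misgraded. The documents give no misgrading rate, no direction and no CO2 rate, so these figures show sensitivity and are not an estimate. The finding does not depend on them.

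**What to change.** - Name the research assistant's score as the primary score for CO2 versus WE, with the assistant viewing only from the start of withdrawal. Because CO2 is used on withdrawal in all groups, this can largely mask the method.
- State one rule for the score used in the comparisons within WE.
- Keep the operator's score for the agreement analysis and a sensitivity analysis.
- Amend Methods, Mucus scores and Statistical analysis to say that the colonoscopist is blinded to fluid type within WE only.
- If a colonoscopist who did not insert does the grading, or masked video is read, say that instead.

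The cost is protocol wording and a rule on when the assistant starts viewing; the sample size does not change. The grading assistant must not handle or record fluid during insertion. The plan does not assign that task, so whether another person is needed cannot be told from it. Residual fluid may sometimes reveal the method, so masking of the assistant would be good but not perfect.

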## **Participants**

Consecutive patients aged 20-75 years old undergoing colonoscopy for screening, surveillance, and positive fecal immunochemical test will be considered for enrollment. The exclusion criteria will include familial adenomatous polyposis and hereditary non-polyposis colorectal cancer syndrome, active inflammatory bowel disease, previous colonic resection, gastrointestinal bleeding, therapeutic colonoscopy (e.g., hemostasis, removal of large polyp), evidence of colonic obstruction based on pre-colonoscopy clinical evaluation, American Society of Anesthesiology classification of physical status grade 3 or higher, allergy to fentanyl or midazolam, mental retardation, pregnancy, and refusal to provide a written informed consent.

## **Randomization**

Patients will be randomized in a 1:1:1:1 ratio to undergo CO2 insufflation and WE insertions with either water infusion, 50% saline infusion, or 25% saline infusion. Randomization will be carried out by a computer-generated random sequence. Individual random sequences will be placed in an opaque envelope kept by an independent research assistant not directly involved in this study, which will be opened immediately before the procedure.

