### **Sample size estimation**

We performed an observational study focusing on left colon mucus production using CMS scoring system by unblinded colonoscopist and compared either full strength normal saline (normal saline group), 1:1 mixed normal saline/water (50% saline group), or 1:3 mixed normal saline/water

(25% saline group) during WE insertion in patients undergoing routine colonoscopies in December 2020. We compared these findings with the reference WE water group which was video recorded during our previous randomized controlled trial comparing right colon adenoma miss rate using WE and CO2 insufflation. The results showed that fluid containing saline significantly reduced the mucus production compared to water alone (Table 1).

The sample size estimation is based on the assumption that WE 50% saline infusion will reduce left colon mucus score compared to WE water infusion. Mucus score reduction to  $\leq 1$  is considered clinically significant. According to our preliminary data, we estimate the proportion of subjects with CMS score  $\leq 1$  to be 50% in the WE water group. The sample size needed to show the proportion of subjects with CMS score  $\leq 1$  that can be increased to 80% by WE 50% saline infusion at a 5% alpha error level with 90% power will be 68 patients per group. To account for dropouts, incomplete procedures, and inadequate preparation, an additional 10% will be enrolled. Therefore, a total of 300 patients (75 patients in each group) will be enrolled.

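### Neither the allocation nor the primary tests account for which of the two colonoscopists does the case, a modest and cheaply avoided loss of precision

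*Combined protocol and SAP*

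**What the plan says.** All places are in the combined protocol and SAP.

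- **Randomization:** "Patients will be randomized in a 1:1:1:1 ratio", and "Randomization will be carried out by a computer-generated random sequence". Assignments are held in opaque envelopes by an independent assistant, "which will be opened immediately before the procedure". The section names no blocks or strata. It does not say whether the colonoscopist is already assigned when the envelope is opened.
- **Colonoscopy Procedures:** "Colonoscopies will be performed by two board-certified colonoscopists". They are blinded to water versus mixed saline, and infused volume is not capped. Their shares of the cases are not given.
- **Mucus scores:** "the blinded colonoscopist and another blinded research assistant will grade the amount of mucus produced in the left colon", each independently, after the raters have agreed on 10 training videos. The plan states that no validated scale exists. It does not say which of the two scores is the primary one.
- **Sample size estimation:** "a total of 300 patients (75 patients in each group) will be enrolled".
- **Statistical analysis:** overall tests are Fisher's exact and Kruskal-Wallis, followed by pairwise comparisons. Colonoscopist is in neither these tests nor the listed risk factors for the logistic model. Rater agreement is described with Fleiss kappa.

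**The concern.** One two-level variable, which can be known before the procedure, can affect the primary endpoint in two ways. The first is technique: the Statistical analysis section itself lists infusion volume and insertion time as possible causes of mucus, and both depend partly on who holds the scope. The second is rating: on the natural reading of the Mucus scores section, the same person supplies one of the two scores.

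Nothing in the stated plan balances this variable across arms or removes it from the comparison. By chance, one colonoscopist may do noticeably more of one arm than of another, and any difference between the two then appears as part of the difference between arms. What is at stake is precision in the primary comparisons. Infusion volume and insertion time are candidates in the risk-factor regression, but that regression does not change the primary tests.

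**Working it through.** **1. The plan's own figures.** Inputs from Sample size estimation: CMS ≤1 in 50% (water) versus 80% (50% saline), alpha 5% (two-sided assumed), power 90%, 68 per group.

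- Pooled normal formula: n = [1.96·√(2·0.65·0.35) + 1.2816·√(0.25 + 0.16)]² / 0.30² = (1.322 + 0.821)² / 0.09 = 51.0, so 52. With continuity correction it is 58. Fisher's exact test has 90.6% power at 58.
- So 68 does not follow from the stated inputs. The difference is on the safe side, and it is a separate matter.
- The inflation step does reproduce: 68 × 1.10 = 74.8, so 75; 75 × 4 = 300.
- Power at 75 versus 75: (0.30·√75 − 1.322)/0.640 = 1.99, which gives 97.7%.

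**2. How uneven the colonoscopist mix can be.** Assume 75 per arm and an even split of cases between the two. The SD of the difference in one colonoscopist's share between two arms is √(2 × 0.25/75) = 0.082. In simulation, the gap between two given arms reaches 16 points at its 95th percentile. The largest gap across the four arms has median 12 points and 95th percentile 21 points.

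**3. What that does to an arm difference.** The shift is the share gap times the difference between colonoscopists in their CMS ≤1 rate. The documents give no value for that difference, so a range is shown. The ordinary sampling SE for 50% versus 80% is √(0.41/75) = 0.0739, a 95% half-width of 14.5 points. This already contains the operator part. Stratifying removes it:

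| Assumed difference | SD of shift (0.0816 × difference) | 95% range of shift | Share of variance (SD²/0.0739²) | Narrowing of SE (1 − √(1 − share)) |
|---|---|---|---|---|
| 5 points | 0.4 points | ±0.8 | 0.3% | 0.2% |
| 10 points | 0.8 points | ±1.6 | 1.2% | 0.6% |
| 20 points | 1.6 points | ±3.2 | 4.9% | 2.5% |
| 30 points | 2.4 points | ±4.8 | 11.0% | 5.6% |

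**4. Error rates.** Two arms of 75 were simulated with a treatment odds ratio of 4, which is 50% versus 80% when the colonoscopists do not differ. The unadjusted test is the uncorrected chi-square; the stratified test is Cochran-Mantel-Haenszel (CMH).

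| Difference in control arm | Power, nothing stratified | Power, CMH only | Power, allocation and CMH stratified |
|---|---|---|---|
| 20 points | 97.0% | 97.3% | 97.4% |
| 30 points | 95.8% | 96.9% | 96.9% |
| 40 points | 93.6% | 96.0% | 96.0% |

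Type I error with nothing stratified is 5.4 to 5.6% over these differences, against 5.3% with no operator difference at all. Two things follow. Nearly all of the gain comes from the stratified test. And if allocation is stratified while the test is left unadjusted, the test becomes conservative: type I error falls to 4.6% at a 30-point difference and 3.55% at 40 points. The two changes belong together.

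**The case against.** The strongest reply is that the consequence is small. The ±3 to ±5 point shift is not an error on top of the confidence interval; it is already inside the ±14.5 points. The 20 to 30 point difference behind it is assumed, and at 5 to 10 points the shift is only ±0.8 to ±1.6. The plan also has safeguards: a second blinded rater who need not change with the colonoscopist, consensus training before scoring starts, blinding to water versus saline, and colonoscopists experienced in WE. All of this stands, and it limits the point to precision. It does not remove it. Training and a second rater do not equalize technique, kappa describes agreement without adjusting anything, and the plan does not make the assistant's score the primary one.

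It can be said in reply that 50% versus 25% saline is also a primary comparison, and that Table 1 shows only 82% versus 77% there, a gap no larger than the possible shift. But ordinary sampling error for that pair is 1.96·√((0.82·0.18 + 0.77·0.23)/75) = 12.9 points. Sampling error is what limits that comparison, and stratifying would not rescue it.

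A reader might also infer that the sequence is unrestricted, so that arms would often end well short of 75. The documents do not support this. They do not say how the sequence is generated, and a 1:1:1:1 ratio, prepared envelopes and 75 per group are all compatible with a fixed or blocked list. Even at 60 per arm, Fisher's exact test would have 91.3% power for 50% versus 80%.

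**Conclusion.** The point holds as a modest, avoidable loss of precision. For 50% saline versus water, stratifying narrows the standard error by about 2 to 6%. This assumes a 20 to 30 point difference between colonoscopists, an even split of cases and 75 per arm; with a smaller difference the gain is below 1%. The planned effect of 30 points is detected with high power either way.

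A reader might infer that the arm comparisons are biased or that the false-positive rate is inflated. Neither follows. Under proper randomization the imbalance is due to chance, and type I error stays near 5%. It could become systematic only if the colonoscopist were chosen after the envelope was opened. The documents do not say that this happens; they only leave the order unstated.

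**What to change.** 1. In Randomization, state how the sequence is generated, and that the colonoscopist is assigned before the envelope is opened.
2. Stratify the 1:1:1:1 sequence by colonoscopist, in concealed blocks of randomly varied size larger than 4, for example 8 and 12. Blocks of 4 would hold exactly one CO2 case each, and CO2 versus WE is visible to the colonoscopist.
3. In Statistical analysis, stratify the primary comparisons by colonoscopist: Cochran-Mantel-Haenszel for CMS ≤1; the row-mean-scores form with rank scores for the four-arm comparison of the 0–4 score; and van Elteren, which is a two-group test, for pairs. Keep the unstratified tests as supportive.
4. State whose mucus score is primary.

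The cost is two sets of envelopes instead of one, the need to draw from the right set, a few lines of analysis text, and slight remaining predictability of CO2 versus WE within blocks. No patients are added and clinical care does not change. The plan is dated before the March 2021 start, so all of this could be in place for the first patient. If only one part can be adopted, the stratified tests carry nearly all of the gain.
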